2.5 DEFINITION OF END OF STUDY

The end of study for individual participants will occur when one of the following events occurs:

- All participant's final data has been captured.
- The participant is discovered ineligible over the course of the study.
- The participant withdraws consent (at any point of the study).
- The participant dies

The definition for the overall end of study is the completion of all sample analysis and the collection and cleaning of all participant follow up data.

3. IVD MEDICAL DEVICE UNDER INVESTIGATION AND COMPARATOR

3.1 NAME OF THE INVESTIGATIONAL IVD DEVICE

Avantect Pancreatic Cancer Test

3.2 MANUFACTURER OF THE INVESTIGATIONAL IVD DEVICE

ClearNote Health, [name].

3.3 INTENDED PURPOSE AND USE OF THE INVESTIGATIONAL IVD DEVICE

The device is designed to report qualitatively the presence or absence of an abnormal epigenomic and genomic signature that is consistent with the signature in patients with pancreatic cancer. The Avantect test utilises plasma cfDNA to assess whether an individual has a signal associated with the presence of pancreatic cancer. The test uses whole blood collected using Streck Cell-Free DNA BCTs provided in the specimen collection kit. Plasma is isolated from whole blood according to ClearNote Health Standard Operating Procedures (SOPs) from which cfDNA is then extracted. This epigenomic and genomic signature is derived from whole-genome shotgun sequencing of 5hmC enriched cfDNA and total cfDNA employed to detect aberrant changes in 5hmC, cfDNA fragment size and copy number. Avantect testing will only be performed at a single site, at ClearNote Health, San Diego, CA. The test includes specimen collection kit, Avantect test reagents, software, and procedures for the analysis of the epigenomic and genomic signature in cfDNA from plasma. 10 ng of cfDNA is used to generate sequencing libraries. Data from sequenced libraries are processed using a proprietary bioinformatics pipeline developed to detect abnormal epigenomic and genomic signature consistent with pancreatic cancer.

3.4 TRAINING AND EXPERIENCE REQUIRED

The high complexity portion of the Avantect test that includes the isolation of cfDNA to create enrichment libraries for the delivery of a patient report is carried out at ClearNote Health following training SOP in accordance with the US Clinical Laboratory Improvement Amendments licensure and College of American Pathologists accreditation requirements.

The low complexity portion of the Avantect test that includes blood collection and plasma isolation. Blood collection will be executed by sites according to Laboratory Manual. Plasma isolation will be executed by the WISH Laboratory according to specific SOP.

All study site personnel performing blood collection procedures will undergo training (e.g. via the study SIV) and can only perform these tasks when training is complete and duties have been assigned and signed off on the study delegation log.

All study personnel performing plasma isolation procedures will undergo training and can only perform these tasks when training is complete and documented in the study delegation log.

3.5 DEVICE ACCOUNTABILITY

See Appendix IV

4. OVERALL TRIAL DESIGN

A prospective, single blinded interventional randomised controlled multicentre study with a pilot followed by 2 stages of recruitment. Selected pre-existing conditions of interest, STAI, body measurements and blood samples will be collected at enrolment (Baseline (T0)), and at 6 months intervals (T1 and T2)). Three cancer and mortality registry searches will be undertaken by the SCTU study team to assess any cancer diagnosed and deaths during the Follow-up study period (T3) (Figure 1). Cancer registry database will be interrogated using any “C-codes and D-codes” available and data from any cancer type will be collected. Peer reviewed published data by the study team¹² has shown that the vast majority of pancreatic cancer patients are diagnosed, in NOD subjects, within 12 -18 months from type 2 diabetes diagnosis. Therefore, the study strategy is to test NOD patients at baseline (T0) (within 6 months from diabetes diagnosis) and thereafter at 6 and 12 months from T0 to ensure that the Avantect test is used in the period before pancreatic cancer symptoms usually present.

[figure not shown]

Figure 1: SAFE-D visit schedule figure

5. SELECTION AND ENROLMENT OF PARTICIPANTS

5.1 PARTICIPANT ENROLMENT

Participants will be approached to take part in SAFE-D via their GP or SDSC. Electronic Health Record (EHR) searches will be undertaken by the study team at participating GP practices and subjects with a recent diagnosis of DM (within six months) will be eligible for enrolment. Subjects attending SDSCs will also be eligible for enrolment. In addition, participants may self-refer for the study via the SAFE-D booking website. Participants who sign the consent form will be considered enrolled.

The study is expected to enrol 15,000 participants over 36 months, including a six-month pilot study to evaluate recruitment feasibility and to estimate the number of participating sites required, and an interim analysis for futility and efficacy (Stage 1). Participants will remain in the study for 12 months, attending study visits at enrolment (baseline (T0)) and at six (T1) and 12 months (T2) post enrolment. There may be planned recruitment stops between the Pilot and Stage 1 of the study to allow for a data driven 'stop-go' decision should this decision not be concluded in the lead up to Stage 1. Recruitment will continue once the Stage 1 interim analysis requirements have been met and will continue unless that analysis concludes that the intervention is futile. Total study duration is expected to be 7 years including 12 months for analysis and report writing.

5.2 CONSENT

The Principal Investigator (PI) retains overall responsibility for the conduct of the research at their site, including the taking of informed consent of participants. They must ensure that any person delegated responsibility to participate in the informed consent process is duly authorised, trained, and competent to participate.

Consent to enter the trial must be sought from each participant. Information about the study will be available on the study website where participants will also be able to book their initial T0

appointment to attend a local recruitment hub (specified local GP practice or other facility staffed and equipped for participant interactions, consenting and blood sample collection) if they are interested to take part. At the time of the T0 appointment, the clinical study teams at the hub will provide each participant with a full explanation of the study, a Participant Information Sheet, and answer any questions before consent is taken. Informed consent must be obtained prior to the participant undergoing procedures that are specifically for the purpose of the trial.

The right of the participant to refuse to participate without giving reasons must be respected.

After the participant has entered the trial, the clinician remains free to give alternative care to that specified in the CPSP at any stage if he/she feels it is in the participant's best interest, but the reasons for doing so should be recorded.

All participants are free to withdraw at any time from the study procedures without giving reasons and without prejudicing further treatment. Participants must be provided with point of contact where they may obtain further information about the study.

Upon completion of the informed consent form, a copy will be given to the participant, a copy stored in the participant's medical notes, the original filed in the site trial file and a copy of the consent form be sent to the Southampton Clinical Trials Unit (SCTU) using secure transfer systems, such as the University of Southampton's SafeSend service, to allow for central monitoring.

5.3 INCLUSION CRITERIA

1. 50 – 84 years of age at the time of enrolment (within year of birth, not month of birth)
2. Haemoglobin A1c (HbA1c) \geq 48 or 6.5% and/or confirmed type II DM diagnosed within the last 180 days (+20 days flexibility allowance)
3. Willing to provide up to 30 mL of blood for each study visit
4. Willing and eligible to undergo MRI scan (or CT scan if MRI is contraindicated)
5. Understands the study process and is willing to take part in the study and sign the informed consent form

5.4 EXCLUSION CRITERIA

6. Prior type I or type II DM diagnosis > 6 months
7. A history of pancreatic cancer, pancreatic neuroendocrine tumour (pNET) or Pancreatitis
8. Under investigation for or confirmed pancreatic cancer / pancreatic cyst

9. Any known pancreatic surgery (not including ERCP), or other major surgery requiring anaesthesia within 3 months
10. Any invasive solid or haematological cancer in the past 3 years, including cancer recurrence after treatment in the last 3 years
11. Current chronic or acute oral or systemic steroid use within 3 months of initial HbA1c or diabetes diagnosis (estimate rather than accurate)
12. Blood transfusion within 1 month
13. Solid organ transplant recipient
14. Currently pregnant
15. Needing dialysis

6. SPECIMENS

Three peripheral blood samples will be collected from consenting participants according to the study schedule of observations and procedures

- Peripheral blood for Safe-D study related testing or future research - 2 STRECK tubes (20 mL)
- Peripheral blood for future metabolomic research testing – 1 Lithium Heparin tube (6 mL)

Blood collection kits comprehensive of Avantect and metabolomic testing tubes will be provided to the collection sites. (See section 6.1 for storage and analysis of clinical samples)

A detailed Laboratory Manual will be provided to sites which will include details regarding sample preparation, handling, shipping and tracking.

6.1 SAMPLE HANDLING

At each study timepoint 2x10 mL Streck® tubes and 1x6 mL lithium heparin tube will be collected from participants. The 2x10 mL Streck® tubes will be used for the Avantect test or future research depending on the study arm, and 1x6 mL lithium heparin will be used for the evaluation of a pancreatic cancer metabolomic signature.

All blood samples will be posted overnight according to Laboratory Manual using study specific boxes equivalent to Royal Mail Safeboxes, to the agreed laboratory: University of Southampton WISH Laboratory. Samples will be sent from sites pseudo-anonymised and fully labelled with a patient and time-point specific kit ID number together with a test requisition form allowing for patient specific reconciliation once received at the WISH laboratory. All sites will keep a record of all samples collected, stored, and shipped. A detailed Laboratory Manual will be provided to sites which will include details regarding sample preparation, handling, shipping and tracking.

In the event of postal delays, any Streck sample received at WISH laboratory after seven days from date of blood collection will be deemed unsuitable for Avantect testing and participants may be asked to undergo repeat blood draw. If repeat T0 draw is requested it must be completed while the participant is still within 6 months from diabetes diagnosis. If T1 or T2 repeat blood collection is requested, it must be within 28 days of the initial sample collection date. A repeat draw can also be requested if a sample is damaged during transport.

Streck® tubes will be processed to plasma within 24 hours of receipt in the WISH laboratory by trained operators and shipped at agreed frequencies as per the Laboratory Manual to ClearNote Health centralised laboratory (San Diego, California, USA). Streck plasma samples collected from patients randomised to the intervention arm will be analysed and results will be generated within 14 business days of receipt of arriving at Clearnote Health and “detected” test results will be reported to SCTU team by providing Avantect test results via an excel file and individual patient reports via secure file sharing (Safesend.soton.ac.uk). In the event of a sample failing predefined Avantect metrics, (expected failure rate is ~4%), the participant will be asked to return for a repeated draw (if the participant is still within the 28 days time frame from the original blood draw). If the failure happens at T0 and no blood could be collected while the participant is still within 6 months of diabetes diagnosis timeframe the participant will be asked to come back at T1. If the failure happens at T1 or T2 and no re-draw was performed, the participant will remain in study. For participants assigned to the control arm, samples will be kept for future potential Avantect testing and/or future research.

Lithium heparin samples will be processed according to SAFE-D specific SOP at the WISH laboratory and stored for future research within the SAFE-D study (or future ethically approved research).

7. STUDY PROCEDURES

7.1 SCHEDULE OF OBSERVATIONS AND PROCEDURES

Visit:	Baseline (T0)	T1	T2	T3
Time:	Within 6 months from Diabetes mellitus (DM) diagnosis*	6 months after T0	12 months after T0	Three occasions over the study duration from consent (T0)
Eligibility evaluation	X			

Informed consent	X			
Patient Data Collection Interview ^a	X			
STAI questionnaire ^b	X	X	X	
Blood sample collection ^c	X	X	X	
Body measurements ^d	X	X	X	
Electronic Health Record Review ^e	X	X	X	
Cancer and mortality registry review				X

NB: The participant/legal representative is free to withdraw consent at any time without providing a reason. When withdrawn, the participant will continue to receive standard clinical care. Follow up data will continue to be collected (unless the participant/legal representative has specifically stated that they do not want this to happen).

*In the SAFE-D study “date of DM diagnosis” refers to the elevated HbA1c date

a: sex, ethnicity, selected pre-existing conditions of interest, family history of cancer, smoking, vaping, alcohol use

b: 6-item STAI

c: 2x10 mL Streck® tubes, 1x6 mL lithium heparin tube

d: height, weight, waist circumference

e: review of selected pre-existing conditions of interest from EHR summaries when available or participant self-reported.

7.2 RECRUITMENT METHODS

Participants will be identified via the strategies described below.

- **From GP practices identified through a commercial participant recruitment platform**

Commercial recruitment platform collaborators will search patient EHR at participating GP practices (Participant Identification Centres (PICs)) and contact eligible subjects via text, email or letter inviting them to participate with a link to the study website (<https://safe-d.uk> / [Home - Safe-D Clinical Study](#)) where they can access the participant information sheet (PIS) and further information.

Interested subjects can book their T0 appointment at a conveniently located recruitment hub (specified local GP practice or other appropriate locations) via the website or call a member of the clinical study team at the hub for more information and help to book the appointment.

- **From GP practices identified through National Institute of Health and Care Research Regional Research Delivery Networks (NIHR RRDN)**

Patient EHR will be searched by staff at participating GP practices (PICs) identified through the National Institute of Health and Care Research Regional Research Delivery Networks (NIHR RRDN). Eligible subjects will be contacted via text, email or letter inviting them to participate with a link to the study website where they can access the PIS and further information. Interested subjects can book their T0 appointment at a conveniently located recruitment hub (specified local GP practice or other appropriate locations) via the website or call a member of the clinical study team at the hub for more information and help to book the appointment.

- **From Specialist Diabetes Service Centres**

Newly diagnosed diabetes patients referred to SDSCs will be invited to take part in the study. Eligible subjects will be contacted by SDSC staff via email or letter inviting them to participate with a link to the study website where they can access the PIS and further information. Interested subjects can book their T0 appointment at a conveniently located recruitment hub (specified local GP practice or other appropriate locations) via the website or call a member of the clinical study team at the hub for more information and help to book the appointment.

- **Self-referral**

Participants may also self-refer to the study following viewing study information found on the study website, on social media or displayed in Primary Care locations. Interested subjects can book their T0 appointment at a conveniently located recruitment hub (specified local GP practice or other appropriate locations) via the website or call a member of the clinical study team at the hub for more information and help to book the appointment.

7.3 SUBJECT SCREENING PROCEDURES

Frequent reviews of GP electronic health records and SDSC records will be undertaken by commercial recruitment platform collaborators or local research teams to identify eligible subjects. Identified eligible subjects will be contacted by text, email or letter, or approached in person when attending SDSC, with study information and invited to participate.

7.3.1 Screen Failures

Patients with whom the SAFE-D study is discussed but who do not enter the study will be documented in the screening log maintained at each participating site, together with reasons for exclusion/decline. The screening log will be filed in the Investigator Site File (ISF).

7.4 REGISTRATION/RANDOMISATION PROCEDURES

Following informed consent, participants will be assigned a unique patient identification number via an independent, web-based system (www.imedidata.com) by a member of the clinical study team at the hub. This will be in the format of SFD-####-##### with the first four digits consisting of the site code, and the last five digits consisting of sequential numbering provided through imedidata.com. The patient identification number will be added to the signed consent form.

Following their T0 visit, participants will be randomised to the control or intervention arm (1:1 ratio) via www.imedidata.com by a member of the WISH Laboratory team as specified on the delegation log. Participants will not be informed which arm they have been randomised to. The randomisation list will be pre-generated with permuted blocks of differing lengths.

7.5 BLINDING AND PROCEDURES FOR UNBLINDING

7.5.1 Blinding

After the T0 visit, participants will be randomised to either intervention or control arm as described in 7.4. Participants will remain blinded to their allocation unless the condition stated in section 7.5.2 is met.

7.5.2 Planned Unblinding

Only participants in the intervention arm who have Avantect “detected” test results (and their GPs) will be informed of their Avantect test results.

7.6 TRIAL PROCEDURES

7.6.1 Timepoint T0

At enrolment visit participants will give informed consent to participate in the study and complete the following:

Sample collection

- 2x10 mL Streck® tubes
- 1x6 mL lithium heparin

Data collection at sites and transferred securely to SCTU

- NHS number
- Date of birth

Contact details (name, postal and email address) for a select number of participants (to be defined) who have consented to taking part in optional further research related to the health questionnaire.

Data collection at sites and entered into study database (Medidata RAVE)

- Height, weight and waist measurements
- 6-item STAI questionnaire
- Selected pre-existing conditions of interest, concomitant medications, family history, alcohol and smoking status

After T0 visit, participants will be randomised to either the control or intervention arm. GPs will be notified if patients under their care are taking part in the study but will remain blinded at this stage.

7.6.2 Timepoint T1 (6 months after T0):

Sample Collection:

- 2x10 mL Streck® tubes
- 1x6 mL lithium heparin

Data Collection:

- 6-item STAI Inventory questionnaire
- Selected pre-existing conditions of interest and concomitant medications
- Weight and waist measurements

7.6.3 Timepoint T2 (12 months after T0):

Sample Collection:

- 2x10 mL Streck® tubes
- 1x6 mL lithium heparin

Data Collection:

- 6-item STAI Inventory questionnaire
- Selected pre-existing conditions of interest and concomitant medications
- Weight and waist measurements

7.6.4 Timepoint T3 (2 years after T2)

T3 refers to the three years of follow-up (following recruitment at T0) which will be collected via linkage with the cancer and mortality registry. At the time of writing the cancer registry is managed by the National Cancer Registration and Analysis Service which sits within NHS England, and the mortality register is managed by the Office for National Statistics but can be accessed through NHS England. Cancer and mortality registry data will still be required and sought even if the owner of the dataset changes in the future. A cancer and mortality registry download will be obtained on three

occasions: once 6,400 participants have been recruited, once 15,000 participants have been recruited, and at 3 years post last participant recruited.

Data Collection from Cancer Registry:

- Any cancer diagnosis (ICD10 C00-D48)
- Date of cancer diagnosis
- Site of cancer diagnosis
- Stage of cancer at diagnosis
- Histology of cancer
- Survival status
- Cancer treatments

Data Collection from Mortality Registry:

[figure not shown]
- Date of death
- Causes of death

The local site study team will collect and keep NHS number, address and contact details (including 1 or 2 phone numbers and an email address) from all participants. NHS numbers and dates of birth for all participants will be shared securely by site to the SCTU. SCTU will then pass on the NHS numbers and dates of birth to the administrators at the registries to allow them to perform registry searches on three occasions during the study. The local site team will also share with the SCTU study team, via secure email, the contact details (name, postal and email address) for a select number of participants (numbers to be defined) who have consented to optional further research questionnaire.

Addresses will be used by sites to contact participants with any Avantect “Detected” results by post. Phone numbers will be used by sites to contact participants if required throughout the study, including contacting participants to inform them of a “Detected” Avantect test if deemed more appropriate than by post alone (at the discretion of the clinical team).

NHS numbers should be shared with the SCTU study team securely either via secure email such as [contact] or SafeSend (<https://safesend.soton.ac.uk/>). SafeSend is a safe and secure (data protection compliant) mechanism for the sites to send the relevant contact information to the SAFE-D email account as it is hosted by the University of Southampton and supports both in-transit and at-rest encryption. Whilst stored at the SCTU, details will be stored securely in a restricted access folder on the University of Southampton managed resource fileshare, in accordance with all applicable data protection regulations.

7.7__ AVANTECT TEST RESULT MANAGEMENT SCHEMA

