2. CLINICAL PERFORMANCE STUDY OBJECTIVES AND ENDPOINTS

2.1 PRIMARY STUDY OBJECTIVES

The study will be divided into a pilot and two stages:

- Pilot: The goal of the six-month pilot is to determine if the enrolment strategy (identifying eligible subjects via commercial recruitment platforms, NIHR Research Delivery Network Primary Care Networks and Specialist Diabetes Service Centres (SDSC)) is adequate, and to identify barriers and develop mitigation strategies to improve recruitment. Participants may also self-refer to the study following viewing study information found on the study website or displayed in Primary Care locations. The pilot will also assess the BMI distribution to determine whether body mass index (BMI) should be included as eligibility criteria in study stage 1 and 2. We will aim to open up to 450 Participant Identification Centres (PICs) during the pilot and at least 30 recruitment hubs where participants can attend for study visits (also referred to as sites).
- The pilot will be considered successful if:
 - Recruitment rate is greater than 10% of invitation to enrolment, or
 - 800 participants are enrolled, or
 - Enrolment is greater than an average of 133 participants per month in the last three months of pilot
- The feasibility of continuation to study stage 1 and 2 will be assessed by the Trial Steering Committee based on recruitment during the pilot
- Study stage 1 will enrol an additional 5,600 NOD participants with the primary objective to evaluate sensitivity and specificity of the Avantect test in detecting pancreatic cancer in 3,200 intervention arm participants with 1 year of follow-up for futility and efficacy.
- Study stage 2 will enrol an additional 8,600 participants to make a total of 15,000 NOD participants with the primary objectives of evaluating sensitivity and specificity of the Avantect test in detecting pancreatic cancer in intervention arm participants, and comparing the proportion of pancreatic cancers deemed resectable across the intervention and control arms.

2.2 PRIMARY ENDPOINTS:

- Pilot: Recruitment rate - number of NOD individuals enrolled into the study divided by the number of individuals invited to participate.
 - Recruitment rate to be greater than 10% of invitation to enrolment OR
 - 800 participants are enrolled OR
 - Enrolment is greater than an average of 133 patients per month in the last 3 months of the pilot.
- Study stage 1 and 2:

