7.12 TRIAL INTERVENTION DISCONTINUATION AND PARTICIPANT WITHDRAWAL

Participants with abnormal imaging results (cancer diagnosis) will discontinue further study visits but cancer and mortality registry searches will be completed as planned.

Participants will be able to withdraw from the study at any time and this will be recorded on the study database. It should be ascertained and documented whether the participant wishes to;

1. withdraw from future study procedures but allows for new data/information to be collected and already collected data and samples to be retained for analysis.
2. withdraw from future study procedures including collection of new data but allows for already collected data and samples to be retained for analysis.
3. completely withdraw, i.e. withdraw from future study procedures and requests that any remaining samples are disposed of and no further data will be collected.

A complete withdrawal from the trial should be recorded as end of study for the participant in the relevant eCRF and in their medical record and no further data should be collected for this participant. Already collected data will be retained to protect the validity of the study in line with HRA guidance.

If participants withdraw consent for further study procedures but are willing to continue sharing information it would remain useful for the trial team to continue to collect any routine data (i.e., data that can be collected with no impact on the participant beyond standard clinical care/follow-up), and this will continue unless the participant explicitly requests otherwise.

In any case, participants who completely withdraw or withdraw only from further study procedures should revert to standard clinical care/follow-up as deemed by the responsible clinician.

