An analysis for futility and efficacy will be conducted once 3,200 individuals randomised to the intervention arm have returned for the third blood-draw (T2) in order to obtain cancer outcome data from the cancer registry. This amounts to 43.8 % of the total information accrual in the intervention arm, accounting for 2.5% not qualifying for the Per Protocol population (see 9.4; $3,200/7,312$). All individuals with one or more Avantect “detected” test results will be included as positive predictions. Individuals whose Avantect test results are all “not detected” will be included as negative predictions. Based on a cumulative one-sided alpha of 0.05 and 96.5% power for the three co-primary outcomes, the futility and efficacy thresholds at stage 1 interim analysis are detailed in the table below. If all study endpoints are deemed futile, or in the scenario that all study endpoints are deemed efficacious the study will stop at this stage. If all of the study endpoints are deemed promising then the study will continue to stage 2. If there is a combination of results, the Trial Steering Committee (TSC) and IDMC will decide whether the study progresses to stage 2.

	Expected proportion	Futility threshold at stage 1	Promising result range at stage 1	Efficacy threshold at stage 1
Sensitivity	65%	<46.5%	46.5% to 63.1%	>63.1%
Specificity	95%	<92.0%	92.0% to 94.9%	>94.9%
Resectability	40%	<21.0%	21.0% to 38.1%	>38.1%

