9.3 STUDY TIMEPOINTS

There will be three timepoints for blood collection: at baseline (T0), 6 months +/- 2 weeks post-baseline (T1), and 12 months +/- 2 weeks from baseline (T2). For each study timepoint, the Avantect test will be conducted. For samples collected from participants assigned to the intervention arm, the Avantect test will be assessed as soon as possible within 14 business days of receipt of samples in the analysing laboratory at ClearNote Health. Those with positive test results (test result = Avantect “detected”) in the intervention arm will undergo diagnostic pancreas imaging. Samples collected from participants assigned to the Control arm will be stored for potential future Avantect testing or future research.

The study design comprises a pilot and two study stages:

- Stage 1 Analysis will be carried out 6 months after the T1 visit for 3,200 participants in the intervention arm. Only participants followed up for a minimum of 6 months after the T1 visit in the intervention arm will be included in this analysis.
- Stage 2 Analysis will be carried out after 3-year follow-up data has been collected for all 15,000 participants.

In addition, during the study annual readouts will be provided to the data monitoring committee to monitor study progress and inform on decisions to continue or stop the study.

The diagnostic performance of the Avantect test results will be summarised according to the pancreatic cancer diagnoses collected by the point of analysis. The stage shift, and resection rate of pancreatic cancer will be summarised by arm. For this purpose, a positive test at any timepoint will be considered a ‘positive prediction’ e.g., if a participant has a negative result at T0, but a positive result at T1, their overall prediction will be considered as at-risk of pancreatic cancer.

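### No scheduled registry download supplies the 12-month outcomes that the Stage 1 interim needs, and the Stage 1 inclusion rule conflicts with sections 9.2 and 9.4

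*Protocol*

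**What the plan says.** Section 7.6.4 of the protocol sets three registry downloads: "once 6,400 participants have been recruited, once 15,000 participants have been recruited, and at 3 years post last participant recruited".

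Three other places describe the Stage 1 dataset:

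- Section 2.1 asks for test accuracy in "3,200 intervention arm participants with 1 year of follow-up for futility and efficacy".
- Section 9.2 triggers the analysis "once 3,200 individuals randomised to the intervention arm have returned for the third blood-draw (T2) in order to obtain cancer outcome data" from the registry. The same paragraph counts every individual with a detected result as a positive prediction.
- Section 9.3 states "Stage 1 Analysis will be carried out 6 months after the T1 visit for 3,200 participants in the intervention arm", and adds "Only participants followed up for a minimum of 6 months after the T1 visit in the intervention arm will be included in this analysis".

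Two further rules bear on who is in the set. Section 7.12 says "Participants with abnormal imaging results (cancer diagnosis) will discontinue further study visits", while registry searches carry on. Section 9.4 runs all analyses on the Per Protocol population, which in the intervention arm needs only one analysable test result.

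**The concern.** Stage 1 is the protocol's only formal interim for futility and efficacy. It needs cancer diagnoses in participants with and without a detected result, and the two groups reach the database by different routes. Detected participants are referred for imaging, and their imaging and pathology reports are collected as study data (7.8.1, 7.9.2). Not-detected participants are neither told their result nor imaged under the study (7.8.2), so their cancers come to light mainly through the registry. A download that is too early loses false negatives more than true positives, which raises apparent sensitivity.

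The inclusion rule is a second problem. If attending T1 is a condition, a participant whose cancer is found from the T0 sample and diagnosed before T1 has no T1 visit and falls out. So does anyone who dies before T1 plus 6 months. Inclusion would then depend on the outcome being measured.

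**Working it through.** **Step 1. The plan's own figures.** Pilot plus Stage 1 is 800 + 5,600 = 6,400, and half of that at 1:1 is 3,200. The information fraction in 9.2 reproduces: 3,200/7,312 = 43.8%.

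**Step 2. The timing gap.** The 6,400th recruit is about the 3,200th intervention participant. T2 is 12 months after T0, so the 9.2 trigger falls about 12 months after the first download. It falls later still if anyone fails to return for T2. This gap does not depend on the pace of recruitment.

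**Step 3. Calendar dates.** Section 5.1 expects 15,000 recruits in 36 months, including a six-month pilot.

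- Assumption A, 800 in 6 months and then even accrual: 14,200/30 = 473 per month. The 6,400th is reached at 6 + 5,600/473 = month 17.8, and the 12-month point at month 29.8.
- Assumption B, even accrual throughout: 15,000/36 = 417 per month. The 6,400th is reached at month 15.4, and the 12-month point at month 27.4.

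The second download is at month 36 under both. It would precede Stage 1 only if the remaining 8,600 were recruited within 12 months, that is at more than 8,600/12 = 717 per month.

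**Step 4. What the first download would contain.** Mean follow-up under A is (800 × 14.8 + 5,600 × 5.9)/6,400 = 7.0 months.

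| | A | B |
|---|---|---|
| Mean follow-up (months) | 7.0 | 7.7 |
| Participants with 12 months | 12% | 22% |
| Share of the first 12 months of person-time covered | 56% | 61% |

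**Step 5. Illustration of the early download.** Assume that all test-detected cancers are known from study reports and that a fraction c of test-negative cancers is captured. For true sensitivity s:

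apparent sensitivity = s / (s + (1 − s)c)

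- With s = 65%, c = 80%, 60% and 40% give 70%, 76% and 82%.
- The 63.1% efficacy threshold is exceeded when c < s(1 − 0.631) / (0.631(1 − s)). For s = 49%, the value to be ruled out in 9.4, this is 0.49 × 0.369/(0.631 × 0.51) = 0.56. For s = 42%, the value in 9.2, it is 0.42.
- Resectability: assume 14% in missed cancers. A 40% overall rate then implies (0.40 − 0.35 × 0.14)/0.65 = 54% in detected cancers. At c = 50% the overall rate reads (0.65 × 0.54 + 0.175 × 0.14)/0.825 = 46%.

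**Step 6. Illustration of the inclusion rule, true sensitivity 65%.**

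| Dropped | Apparent sensitivity |
|---|---|
| 25% of true positives only | 58% |
| 50% of true positives only | 48% |
| 25% of false negatives only | 71% |
| 50% of false negatives only | 79% |
| Equal shares of both | 65% |

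Dropping 25% or 50% of true positives only takes resectability from 40% to 37% or 33%, on the Step 5 split.

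**Step 7. How few cases decide the category.** Applying 1% to 3,200 gives 32 cancers. That is an upper figure, because 9.2 gives 1% over three years. One unseen false negative moves 20/32 = 62.5% (promising) to 20/31 = 64.5% (efficacious). One dropped true positive moves 15/32 = 46.9% (promising) to 14/31 = 45.2% (futile, below 46.5%).

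**The case against.** The statistics section already has the right timing. Section 9.2 waits for T2 precisely so that registry outcomes can be obtained, and 9.3 works with diagnoses collected by the point of analysis. On this view 7.6.4 is a loose sentence, and the bias in Step 5 arises only if the team uses the early download regardless. If the analysis were run at that download under the 9.3 rule, only about 12% of participants would qualify (assumption A), all of them with 12 months. This has force against the size of the illustration. It does not remove the conflict: 7.6.4 limits the downloads to three, none falls where 9.2 needs it, and its third download states its lag expressly, so a 12-month lag cannot be read into the first.

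On inclusion, a reader might infer that everyone diagnosed or dead before month 12 is dropped. The documents do not support that. A living participant diagnosed between T1 and month 12 remains under registry follow-up and can meet 9.3. The T2 return in 9.2 is a trigger and not a membership rule. Sections 9.2 and 9.4 would keep the others too, and 9.3 could be meant as elapsed time, since T1 is scheduled 6 months after T0. What stands is a literal rule in 9.3 that excludes diagnoses before T1 and deaths before T1 plus 6 months, against two sections that include them.

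A reader might also infer that one distorted endpoint would stop the trial. Under 9.2 it stops only if all three endpoints are futile or all three are efficacious. Mixed results go to the TSC and IDMC, who would nonetheless be judging from these figures.

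**Conclusion.** The timing conflict holds on the text. The first download precedes the required follow-up by about 12 months at any recruitment pace. That the second comes too late rests on the planned 36-month recruitment and would fail only above about 717 recruits per month. As written, no scheduled download delivers the interim outcomes.

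The inclusion rule is a conflict between sections, and its literal reading in 9.3 depends on outcome for early diagnoses and deaths.

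Bias in interim sensitivity and resectability is credible but not quantified by the protocol. The percentages in Steps 5 and 6 rest on assumed capture and exclusion shares. The two effects can oppose each other, and deaths may remove false negatives as well as true positives, so neither the net direction nor the size can be stated. With at most about 32 cancers expected, even one misplaced case can change the interim category.

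**What to change.** - **Section 7.6.4:** tie the first download to at least 12 months after the 3,200th intervention participant is randomised, plus a stated allowance for registration lag. The protocol gives no lag. At the planned pace an allowance of up to 36 − 29.8 = 6.2 months (8.6 months under even accrual) still puts this download before the second.
- **Sections 9.2 and 9.3:** define the Stage 1 set as all Per Protocol intervention participants randomised at least 12 months before the data cut, regardless of T1 or T2 attendance, diagnosis or death. Apply one diagnosis cut-off date to detected and not-detected participants alike.

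The cost is one re-dated registry request and a few reworded sentences, and the number of downloads stays at three. The downside is that the first linkage comes about a year later, so any annual readout to the data monitoring committee before then has no registry data. The 12-month wait itself adds nothing to the Stage 1 date that 9.2 already sets, but the lag allowance may delay it.
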